7.1.1.1 Group 1: Dose Escalation of BMS-986156 when combined with ipilimumab

Treatment group 1: A modified 3+3 dose escalation then expansion to a total of 10 patients per arm (escalation + expansion, if applicable) will be performed on two dose levels of this combination therapy.

- The first 3 subjects will be enrolled at dose level 1 (3 mg/kg ipilimumab + 30 mg BMS-986156).
 - If 0 out of these 3 patients have a DLT, 3 patients will then be enrolled on dose level 2 (3 mg/kg ipilimumab + 100 mg BMS-986156).
 - If 1 of 3 subjects have a DLT in dose level 1 (30 mg), 3 more patients will then be enrolled at this dose level. If only 1 of the 6 total subjects at dose level 1 has a DLT, then 3 patients will then be enrolled on dose level 2, 100 mg BMS-986156.
 - Additionally, 4 patients will be enrolled on dose level 1 to a total of 10 patients at 30 mg BMS-986156.
 - If 2 of 3 subjects have a DLT at dose level 1, then dose escalation is stopped and the MTD is reached (dose level 1).
- Subjects will be receiving 3 mg/kg ipilimumab + 100 mg BMS-986156 at dose level 2.

- At this dose level, if 0 of the 3 subjects have a DLT, then both dose level 1 and dose level 2 will be expanded to more patients so that each arm has a total of 10 patients enrolled.
- If 1 of the 3 subjects at dose level 2 have a DLT, 3 more subjects will then be enrolled at this dose level. If only 1 of the 6 total subjects at dose level 2 have a DLT, both dose level 1 and dose level 2 will be expanded to more patients so that each arm has a total of 10 patients enrolled. If 2 of the 6 total subjects at dose level 2 have a DLT, then dose escalation is stopped and the MTD is reached (dose level 1). Only dose level 1 will be expanded to a total of 10 patients enrolled.
- If 2 of 3 subjects at dose level 2 have a DLT, then dose escalation is stopped and the MTD is reached (dose level 2).
- The expansion phase dose will be selected based on safety and response readouts. For example, the dose exhibiting the best therapeutic response or pharmacodynamic profile with the best safety profile.

Dose Escalation of BMS-986156 when combining with Ipilimumab.

Dose Level 1 3 mg/kg Ipilimumab + 30 mg BMS-986156

Dose Level 2 3 mg/kg Ipilimumab + 100 mg BMS-986156

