7.1.1.2 Group 2: Dose De-Escalation of BMS-986156 when combined with ipilimumab plus SBRT

BMS-986156 dose as determined in group 1, for combination treatment with ipilimumab, before adding SBRT to the treatment regimen.

Treatment group 2: A modified 3+3 dose de-escalation then expansion to a total of 20 patients will occur at the MTD.

The first 3 subjects will be enrolled at dose level 1 (3 mg/kg ipilimumab + BMS-986156).

- If 0 out of these 3 patients have a DLT, 3 additional patients will then be enrolled on this same dose level.
- If 1 of 3 subjects have a DLT, 3 more patients will then be enrolled at this dose level. If only 1 of the 6 total subjects at dose level has a DLT, then this dose level will be considered safe and all other patient in this arm will be treated at this dose level.
- If 2 of 6 subject have DLT at dose level 1, then the dose will be de-escalated as per table below.
- If 2 of 3 subjects have a DLT at dose level 1, then the dose will be de-escalated as per table below

Dose De-Escalation of Ipilimumab when combining with BMS-986156 plus SBRT.

If MTD from group 1 finds the 30mg BMS-986156 then:

Dose Level 1 3 mg/kg Ipilimumab + 30 mg BMS-986156

Dose Level -1 1 mg/kg Ipilimumab + 30 mg BMS-986156

If MTD from group 1 finds the 100mg BMS-986156 then:

Dose Level 1	3 mg/kg Ipilimumab + 100 mg BMS-986156
Dose Level -1	1 mg/kg Ipilimumab + 100 mg BMS-986156
Dose Level -2	1 mg/kg Ipilimumab + 30 mg BMS-986156

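### Group 1's rule names 100 mg the MTD after 2 of 3 DLTs at that dose but 30 mg after 2 of 6, and group 2's starting dose follows that MTD

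*Combined protocol and SAP*

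**What the plan says.** Section 7.1.1 of the combined protocol and SAP describes a 3+3 design whose purpose is to find the MTD. Group 1 has two levels, both with ipilimumab 3 mg/kg: level 1 is 30 mg BMS-986156 and level 2 is 100 mg. Level 2 opens only after 0 of 3 or 1 of 6 DLTs at level 1.

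For level 2, section 7.1.1.1 gives four results. After 0 of 3 or 1 of 6 DLTs, "both dose level 1 and dose level 2 will be expanded to more patients", to 10 each, and no MTD is named. "If 2 of the 6 total subjects at dose level 2 have a DLT, then dose escalation is stopped and the MTD is reached", with dose level 1 given in brackets as the MTD, and only level 1 is expanded. The last branch says that if "2 of 3 subjects at dose level 2 have a DLT, then dose escalation is stopped and the MTD is reached (dose level 2"). A further sentence adds: "The expansion phase dose will be selected based on safety and response readouts".

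Section 7.1.1.2 says that group 2 takes its BMS-986156 dose from group 1 and that "expansion to a total of 20 patients will occur at the MTD". It has two tables, one for each possible MTD. The second is headed "If MTD from group 1 finds the 100mg BMS-986156 then" and starts at 3 mg/kg ipilimumab with 100 mg BMS-986156, now with SBRT.

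**The concern.** The two failing branches at 100 mg point in opposite directions. Two DLTs in six patients send the MTD down to 30 mg, while two DLTs in three patients, twice the observed rate, leave it at 100 mg. A 3+3 rule should step down in both cases.

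The first primary objective (section 2.1) is to find the safe BMS-986156 dose, 30 mg or 100 mg, with ipilimumab. Group 2, planned at 20 patients, takes the answer into a regimen that adds SBRT. Followed as written, the 2 of 3 branch would open the 100 mg table in group 2 straight after 100 mg had failed without radiation. Section 3.3 states that there are no clinical data on the safety of BMS-986156 with ipilimumab, so this rule is what decides the dose.

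**Working it through.** The plan states no operating characteristics for its dose-finding rule, so there is no figure of its own to reproduce. The check is a comparison of the text followed by a short calculation.

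**1. Results at dose level 2 in section 7.1.1.1**

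| DLTs at 100 mg | Observed rate | MTD named |
|---|---|---|
| 0 of 3 | 0% | none; both levels expanded |
| 1 of 6 | 17% | none; both levels expanded |
| 2 of 6 | 33% | level 1 (30 mg) |
| 2 of 3 | 67% | level 2 (100 mg) |
| 3 of 3, or 3 or 4 of 6 | 50% to 100% | no rule written |

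The bracketed level cannot simply mark where escalation stopped. In the 2 of 6 branch escalation also stops at level 2, yet the bracket names level 1.

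**2. Does another section correct the 2 of 3 branch?**

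- Section 1 (group 2 paragraph) opens group 2 at 2 of 6 DLTs or fewer, and otherwise once 10 patients have been treated in group 1. This sets the timing and not the dose.
- Sections 7 and 7.1 say that the dose comes from group 1, without saying how.
- Section 10.1 stops a level when more than 33% of the expanded group have DLTs and falls back to the next lower level. The 2 of 3 branch orders no expansion of level 2, so this rule is not clearly triggered.
- Section 10 requires IND Office approval before a dose level changes. This is oversight and not a decision rule.
- Sections 7.1.1.2 and 7.1.1.3 de-escalate after 2 of 3 and after 2 of 6 alike. They show what the authors probably meant, but they govern groups 2 and 3.

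**3. How likely is the branch?**

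Let p be the true DLT rate at 100 mg and q = 1 − p. All chances are conditional on level 2 being opened. The values of p are assumptions.

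- Exactly 2 of 3: 3p²q. At p = 0.10, 3 × 0.01 × 0.90 = 0.027. At 0.20, 3 × 0.04 × 0.80 = 0.096. At 0.40, 3 × 0.16 × 0.60 = 0.288. At 0.50, 3 × 0.25 × 0.50 = 0.375.
- Exactly 2 of 6 (1 of 3, then 1 of 3): (3pq²)². At p = 0.20, 0.384² = 0.147.
- 3 of 3: p³.
- 3 or 4 of 6 (1 of 3, then 2 or 3 of 3): 3pq² × (3p²q + p³). At p = 0.20, 0.384 × 0.104 = 0.040.

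| Assumed p | 2 of 3 (names 100 mg) | 2 of 6 (names 30 mg) | 3 of 3 (no rule) | 3 or 4 of 6 (no rule) |
|---|---|---|---|---|
| 10% | 2.7% | 5.9% | 0.1% | 0.7% |
| 20% | 9.6% | 14.7% | 0.8% | 4.0% |
| 40% | 28.8% | 18.7% | 6.4% | 15.2% |
| 50% | 37.5% | 14.1% | 12.5% | 18.8% |

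The remainder of each row is the chance that 100 mg passes. Over this range, the chance that 100 mg is named the MTD rises with its toxicity, because the only branch that names it is a failing one.

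**The case against.** The strongest reply is that this is a one-line slip for dose level 1 that no competent team would follow. That is probably how it arose. There are also real safeguards: a safety report after every 3 evaluable patients, IND Office approval before dose changes, and group 2's own 3+3 check. A reader should therefore not infer that 20 patients would go through on a failed dose. What stands is that the written instruction is wrong and that those applying the safeguards would be working from it.

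A reader might also infer that group 2 has no usable table when both levels pass, since no MTD is then named. The documents do not support that. Sections 3.1.2 and 3.1.4 treat a tolerated top dose as one at which no MTD was reached. Section 5.2.10 provides for either 30 mg or 100 mg as the dose determined in group 1, the opening line of section 7.1.1.2 uses the same idea, and section 7.1.1.1 says how a dose is chosen after expansion. The MTD in group 2's table headings is best read as shorthand for that dose. The remaining gap is small: the selection sentence speaks of the expansion phase and does not mention group 2.

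Nor is it a defect in itself that group 2's 100 mg table lowers ipilimumab first, to "1 mg/kg Ipilimumab + 100 mg BMS-986156". The table is titled as an ipilimumab de-escalation. The background sections report more high-grade toxicity at higher ipilimumab doses and no MTD for BMS-986156 up to 800 mg. The restriction in section 7.2.1 to DLTs in the irradiated organ is a separate matter, since the same list goes on to include general events.

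**Conclusion.** The point holds for the 2 of 3 branch at dose level 2. It contradicts the 2 of 6 branch beside it, nothing elsewhere corrects it, and section 7.1.1.2 would carry 100 mg into group 2 with SBRT. The chance of landing on the branch, once level 2 is open, is 2.7% at a true DLT rate of 10% and 37.5% at 50%. These figures assume independent patients with a common DLT rate, and the rates themselves are assumed.

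Two smaller points go with it. Outcomes worse than those listed (3 of 3, and 3 or 4 of 6) have no written rule. When 100 mg passes, one linking sentence is missing; that is a gap in wording and exposes nobody to a failed dose. The plan does not make 100 mg the default when both levels pass, and nothing here argues that it should.

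**What to change.** In section 7.1.1.1, for dose level 2:

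- Change the 2 of 3 branch so that 2 or more DLTs in 3 patients stop escalation and make dose level 1 the MTD.
- Change the 2 of 6 branch to 2 or more of 6, with the same result.

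As a secondary clarification, add one sentence, cross-referenced in section 7.1.1.2. When 100 mg passes with 0 of 3 or 1 of 6 DLTs, group 2's starting dose and table follow the dose chosen under the existing safety-and-response sentence. The choice is limited to levels that passed and have not met the more-than-33% rule of section 10.1. This keeps the sponsor's selection rule as it is.

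The sponsor should also look at the matching branch at dose level 1, where 2 of 3 DLTs make 30 mg the MTD although group 1 has no lower dose, and reconcile it with the group 2 opening rule in section 1.

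The cost is a text correction, with no extra patients or visits.

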7.1.1.2 Group 2: Dose De-Escalation of BMS-986156 when combined with ipilimumab plus SBRT

BMS-986156 dose as determined in group 1, for combination treatment with ipilimumab, before adding SBRT to the treatment regimen.

Treatment group 2: A modified 3+3 dose de-escalation then expansion to a total of 20 patients will occur at the MTD.

The first 3 subjects will be enrolled at dose level 1 (3 mg/kg ipilimumab + BMS-986156).

- If 0 out of these 3 patients have a DLT, 3 additional patients will then be enrolled on this same dose level.
- If 1 of 3 subjects have a DLT, 3 more patients will then be enrolled at this dose level. If only 1 of the 6 total subjects at dose level has a DLT, then this dose level will be considered safe and all other patient in this arm will be treated at this dose level.
- If 2 of 6 subject have DLT at dose level 1, then the dose will be de-escalated as per table below.
- If 2 of 3 subjects have a DLT at dose level 1, then the dose will be de-escalated as per table below

Dose De-Escalation of Ipilimumab when combining with BMS-986156 plus SBRT.

If MTD from group 1 finds the 30mg BMS-986156 then:

Dose Level 1 3 mg/kg Ipilimumab + 30 mg BMS-986156

Dose Level -1 1 mg/kg Ipilimumab + 30 mg BMS-986156

If MTD from group 1 finds the 100mg BMS-986156 then:

Dose Level 1	3 mg/kg Ipilimumab + 100 mg BMS-986156
Dose Level -1	1 mg/kg Ipilimumab + 100 mg BMS-986156
Dose Level -2	1 mg/kg Ipilimumab + 30 mg BMS-986156

 - If 1 of 3 subjects have a DLT in dose level, 3 more patients will then be enrolled at this dose level. If only 1 of the 6 total subjects at dose level has a DLT, then this dose level will be considered safe and all other patient in this arm will be treated at this dose level.
 - If 2 of 6 subject has DLT then the dose will be de-escalated as per table below.
 - If 2 of 3 subjects have a DLT at dose level 1, then the dose will be de-escalated as per table below

Dose De-Escalation of BMS-986156 when combining with Nivolumab plus SBRT.

Dose Level 1	480mg Nivolumab + 30 mg BMS-986156
---------------------	------------------------------------

Dose Level -1 480mg Nivolumab + 10 mg BMS-986156**7.1.2. Reinduction for all arms**

Reinduction will be allowed for patients in which the treating physician feels there was benefit from the trial treatment. It will consist of repeating the original treatment using the same schedule for each arm. Radiation may be given during reinduction, but is not required. Pending the treating radiation oncologist judgment, additional radiation therapy to a previously non-irradiated lesion can be administered during re-induction. Timing of radiation during reinduction will be at the discretion of treating Radiation Oncologist.

The target lesion for radiation will be chosen by the treating radiation oncologist. The target lesion must not have been previously irradiated. The target lesion does not have to be within the same organ that was initially treated during the initial treatment (e.g. patients who received initial lung lesion irradiation can have liver or a bone lesion irradiated during re-induction). Radiation dose and fraction will be either at the initial dose (50 Gy in 4 fractions or 60 Gy in 10 fractions) or at a lower palliation dose (30 Gy in 10 fractions) and may also be combined with low dose radiation ranging from 200cGy-1000cGy in multiple fractions, at the discretion of the treating radiation oncologist.

Other tumor sites may be treated for palliation concurrently or sequentially if needed at the discretion of the treating radiation oncologist.

Reinduction will be allowed after the 4th cycle of systemic imaging (CT, MRI, Ultrasound, or x-ray) to assess the global disease burden will be conducted. If disease control is once again observed (SD or PR by ir-RC, compared to the original pretreatment baseline imaging) without severe (Grade >3) toxicity then patients will be eligible for a second round of reinduction therapy to given in the same manner as the first round of treatment. Patients may continue to have additional rounds of reinduction therapy until PD is observed at their post cycle 4 imaging or severe toxicity (Grade >3) occurs.

7.2. Definition of Dose-Limiting Toxicity:**DLT time frames:**

- Group 1: The time frame for DLT assessment will be within 29 days of therapy initiation in the ipilimumab/BMS-986156 group

Group 2: within 43 days of therapy initiation in the sequential arm (ipilimumab/BMS-986156/radiation)

- Group 3: within 29 days of therapy initiation in the nivolumab/BMS-986156 concurrent group
- Groups 1 (ipilimumab + BMS-986156) and 2 (ipilimumab + BMS-986156 + radiation): Patients will get DLT assessments done every other week (14 ± 3 days after the drug infusion) during the DLT period. When patient is unable to make a clinic visit, a visit to a local healthcare provider must be done for DLT assessment. A report and lab test results must be provided to the trial treating physician or to the trial PI. This will be done case by case in association with the local physician of the patient.

7.2.1. Dose Limiting Toxicity (DLT):

DLT is defined as any:

Group 1 DLT definition:

- Any ≥ Grade 3 bronchospasm or other hypersensitivity reactions lasting for >6h;
- Any other ≥ Grade 3 non-skin related adverse event with the exception of laboratory abnormalities that is asymptomatic, not requiring hospitalization, responsive to supplementation within 24 hours).
- Any Grade 4 laboratory abnormalities, except AST, ALT, or total bilirubin;
 - AST or ALT > 8 x ULN,
 - Total bilirubin > 5 x ULN;
 - AST or ALT > 3 x ULN AND Total Bilirubin > 2 X ULN (Potential drug-induced liver injury as defined by Hy's Law)
- Grade 3/4 rash if no improvement (i.e. resolution to ≤Grade 1) after a 1-2 week infusion delay. Use of topical steroids is permitted.
- Any other Grade 4 adverse event;
- Any adverse event, laboratory abnormality or intercurrent illness which, in the judgment of the investigator, presents a substantial clinical risk to the subject with continued study drug dosing;
- Any motor neurologic toxicity ≥ Grade 3 regardless of causality;
- Any ≥ Grade 3 treatment-related sensory neurologic toxicity.
- Combination related toxicity, such as infusion reactions, diarrhea, colitis, etc., that prevents administration of ipilimumab/BMS-986156 for > 21 days and/or nivolumab/BMS-986156 for > 28 days from the scheduled dose.
- Any clinically ≥ grade 3 non-hematologic toxicity as defined in the NCI CTC v4.0, expected and believed to be related to the combination of study drug and radiation (except nausea and vomiting, diarrhea and electrolyte imbalances responsive to appropriate regimens, alopecia or fatigue lasting less than 7 days).
- Grade 3 Febrile neutropenia
- Any grade 4 neutropenia (with or without fever and/or sepsis) or thrombocytopenia (without bleeding) lasting at least 1 week or longer (as defined by the NCI-CTC v4.0).
- Any of the Grade 4 hematologic adverse events for >7 days.
- Any ≥ grade 3 nausea or vomiting lasting > 5 days despite anti-emetics regimens or ≥ grade 3 diarrhea refractory to anti-diarrhea medications, >48 h.
- Any Grade 2 drug-related uveitis or eye pain or blurred vision that does not respond to topical therapy and does not improve to Grade 1 severity ≤2 weeks OR requires systemic treatment. Any other grade 3 non-hematologic toxicity including symptoms/signs of vascular leak or cytokine release syndrome; or any severe or life-threatening complication or abnormality not defined in the NCI-CTCAE v4.0 that is attributable to the therapy, with the following EXCEPTIONS:
 - Grade 3 or grade 4 electrolyte abnormalities that are not complicated by associated clinical adverse experiences, last ≤48 hours and either resolve spontaneously or respond to conventional medical intervention
 - Isolated Grade 3 elevation of amylase or lipase not associated with clinical or radiographic evidence of pancreatitis
 - Isolated Grade 3 fever not associated with hemodynamic compromise (eg, hypotension, clinical or laboratory evidence of impaired end-organ perfusion)

- Grade 3 endocrinopathy that is well controlled by hormone replacement
- Grade 3 tumor flare (defined as pain, irritation, or rash that localizes to sites of known or suspected tumor)
- Grade 3 fatigue for ≤ 7 days.
-

Group 2 and Group 3 definition of DLTs:

- DLTs used to define the MTD in combination with radiation section 7.1.1.2 and 7.1.1.3 will only use DLTs associated with organ toxicity for the organ irradiated.
- SBRT related adverse events: Any grade ≥ 3 events occurring in radiation volume field will be considered as DLT.
- Any \geq Grade 3 bronchospasm or other hypersensitivity reactions lasting for > 6 h;
- Any other \geq Grade 3 non-skin related adverse event with the exception of laboratory abnormalities that is asymptomatic, not requiring hospitalization, responsive to supplementation within 24 hours).
- Any Grade 4 laboratory abnormalities, except AST, ALT, or total bilirubin;
 - AST or ALT $> 8 \times$ ULN,
 - Total bilirubin $> 5 \times$ ULN;
 - AST or ALT $> 3 \times$ ULN AND Total Bilirubin $> 2 \times$ ULN (Potential drug-induced liver injury as defined by Hy's Law)
- Grade 3/4 rash if no improvement (i.e. resolution to \leq Grade 1) after a 1-2 week infusion delay. Use of topical steroids is permitted.
- Any other Grade 4 adverse event;
- Any adverse event, laboratory abnormality or intercurrent illness which, in the judgment of the investigator, presents a substantial clinical risk to the subject with continued study drug dosing;
- Any motor neurologic toxicity \geq Grade 3 regardless of causality;
- Any \geq Grade 3 treatment-related sensory neurologic toxicity.
- Combination related toxicity, such as infusion reactions, diarrhea, colitis, etc., that prevents administration of ipilimumab/BMS-986156 for > 21 days and/or nivolumab/BMS-986156 for > 28 days from the scheduled dose.
- Any clinically \geq grade 3 non-hematologic toxicity as defined in the NCI CTC v4.0, expected and believed to be related to the combination of study drug and radiation (except nausea and vomiting, diarrhea and electrolyte imbalances responsive to appropriate regimens, alopecia or fatigue lasting less than 7 days).
- Grade 3 Febrile neutropenia
- Any grade 4 neutropenia (with or without fever and/or sepsis) or thrombocytopenia (without bleeding) lasting at least 1 week or longer (as defined by the NCI-CTC v4.0).

- Any of the Grade 4 hematologic adverse events for >7 days.
- Any ≥ grade 3 nausea or vomiting lasting > 5 days despite anti-emetics regimens or ≥ grade 3 diarrhea refractory to anti-diarrhea medications, >48 h.
- Any Grade 2 drug-related uveitis or eye pain or blurred vision that does not respond to topical therapy and does not improve to Grade 1 severity ≤2 weeks OR requires systemic treatment. Any other grade 3 non-hematologic toxicity including symptoms/signs of vascular leak or cytokine release syndrome; or any severe or life-threatening complication or abnormality not defined in the NCI-CTCAE v4.0 that is attributable to the therapy, with the following EXCEPTIONS:
 - Grade 3 or grade 4 electrolyte abnormalities that are not complicated by associated clinical adverse experiences, last ≤48 hours and either resolve spontaneously or respond to conventional medical intervention
 - Isolated Grade 3 elevation of amylase or lipase not associated with clinical or radiographic evidence of pancreatitis
 - Isolated Grade 3 fever not associated with hemodynamic compromise (eg, hypotension, clinical or laboratory evidence of impaired end-organ perfusion)
 - Grade 3 endocrinopathy that is well controlled by hormone replacement
 - Grade 3 tumor flare (defined as pain, irritation, or rash that localizes to sites of known or suspected tumor)
 - Grade 3 fatigue for ≤7 days.
-

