Day 1 and every 21 days: Ipilimumab therapy at 3 mg/kg as a 90 minute intravenous (IV) dose and BMS-986156 (dose as determined in group 1) as a 60 min IV will be given in an outpatient setting. Dose cycles will be repeated every 21 days: on days 1, 22, 43, and 64 for a total of 4 cycles. Nivolumab (480 mg Q4W) will start day 85 and continue every 28 days for 26 cycles. Enrollment of this group will start based on the following criteria. If 2 out of 6 patients, or less, display DLTs, then, enrollment of group 2 can begin. Alternatively, if 3 out of 6 patients, or more, display DLTs, then, enrollment of group 2 cannot begin until 10 patients have been treated in group 1.

SBRT: SBRT will be given after 2 doses of ipilimumab and BMS-986156 on days 29-32 for 50 Gy in 4 fractions or on days 29-40 for 60 Gy in 10 fractions (no SBRT during weekends): SBRT will be directed at 1-4 targetable liver or lung lesion(s). To minimize treatment breaks, patients may start radiation on a Monday.

Group 2

[figure not shown]

Diagram of Treatment Schedule for Ipilimumab + BMS-986156 x 2 → SBRT → Ipilimumab + BMS-986156 x 2 → Nivolumab x 26 (Treatment group 2).

Group 3, 20 patients: Nivolumab + BMS-986156 x 1 + SBRT → Nivolumab + BMS-986156 x 3 → Nivolumab x 22

First dose of Nivolumab + BMS-986156 and SBRT will be given concurrently (early) and followed by Nivolumab + BMS-986156 x 3; then, Nivolumab monotherapy for 22 cycles. Nivolumab will be administered for a total of 26 cycles, either as a combination or monotherapy, in this group. Enrollment of patients for this group will start around the same time as group 1. Choice of treatment group will be at the discretion of PI and treating physician.

Nivolumab therapy at 480 mg dose will be given on day 1 as a 30 minute IV dose and BMS-986156 at 30 mg dose will be given on day 1, 29, 57, 85 as a 60 min IV in an outpatient setting. Nivolumab monotherapy will start on day 113 and will continue for 22 cycles.

SBRT: SBRT will be given on days 1-4 (days 2-5 are acceptable if scheduling does not permit radiation to begin same day as infusions) for 50 Gy in 4 fractions or on days 1-12 for 60 Gy in 10 fractions (no SBRT during weekends). SBRT will be directed at 1-4 targetable liver or lung lesion(s). To minimize treatment breaks, patients may start radiation on a Monday.

Group 3

[figure not shown]

Diagram of Treatment Schedule for Nivolumab + BMS-986156 x 1 + SBRT → Nivolumab + BMS-986156 x 3 → Nivolumab x 22 (Treatment group 3)

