6. **Other toxicities:** Other IRAEs were reported in 2.3-3.8% (Grade 3/4: 0.8-1.5%, Grade 5: 0-0.3%) of subjects receiving 3mg/kg of ipilimumab and in 5.2% (Grade 3/4: 2.2%; Grade 5: 0.6%) of subjects receiving 10mg/kg of ipilimumab. Ocular inflammation, manifested as Grade 2 or Grade 3 episcleritis or uveitis, was associated with concomitant diarrhea in a few subjects (<1%) and occasionally occurred in the absence of clinically apparent GI symptoms. Other presumed IRAEs reported include, but were not limited to, arthritis/arthralgias, pneumonitis, pancreatitis, autoimmune (aseptic) meningitis, autoimmune nephritis, pure red cell aplasia, noninfective myocarditis, polymyositis, and myasthenia gravis, of which were individually reported for <1% of subjects.

5.1.9. Onset and Resolution of IRAEs:

The median time to onset of Grade 3-5 IRAEs in MDX010-20 and Phase 2 studies was 7 to 9 weeks. The time to onset of IRAEs was comparable between the 3- and 10-mg/kg doses. With the recommended treatment guidelines, the median times to resolution of Grades 3-4 IRAEs was 4 to 8 weeks. The time to resolution of IRAEs was comparable between the 3 and 10-mg/kg doses.

5.1.10. Ipilimumab Dose-dependent Safety Profile:

In MDX010-20, immune-related adverse events (irAEs) occurred in 60% of subjects treated with ipilimumab (3mg/kg) and ≥ Grade 3 events occurred in 12-16%. Treatment related AEs leading to discontinuation of therapy were reported in 9.9% of the ipilimumab monotherapy arm

vs 3.0% of the gp100 monotherapy arm. The most common (>1%) treatment related AEs leading to discontinuation in the ipilimumab monotherapy arm were colitis (2.3%), diarrhea (1.5%), and uveitis (1.5%). In a pooled 3mg/kg group from the Phase 2 studies, 8.1% of subjects reported treatment-related AEs leading to discontinuation. The most common were hypopituitarism (2.7%), colitis (1.8%), and decreased appetite (1.8%). In MDX010-20, treatment-related deaths (defined as a treatment-related AE with an outcome of death, reported at any time during the study) were reported in 4 subjects (3.1%) in the ipilimumab monotherapy group, 8 subjects (2.1%) in the ipilimumab plus gp100 group and 2 (1.5%) subjects in the gp100 monotherapy group.

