The Principal Investigator shall obtain all such permissions and authorizations as may be necessary or desirable to allow the collection and use of information protected under federal privacy laws and state privacy laws, including permission/authorization for monitoring and analysis (including re-analysis in combination with results of other studies), for regulatory submission purposes and for applicable reporting (if any).

Tumor response will be determined using the Immune Related Response Criteria (irRC) as described in section 8.3.

The Investigator is responsible for completing an efficacy/safety summary report, and submitting it to the IND Office Medical Affairs and Safety Group, for review and approval. This should be submitted after the first 3 evaluable patients in groups 1 and 3 complete 29 days of study treatment, and after the first 3 evaluable patients in group 2 complete 43 days of therapy initiation, and every 3 evaluable patients per group thereafter. IND Office approval must be obtained prior to advancing/changing dose levels.

A copy of the cohort summary should be placed in the Investigator's Regulatory Binder.

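### The DLT windows in Section 7.2 conflict with the protocol's own delay and rash criteria (mainly in groups 1 and 3) and leave group 2 half of group 3's observation time from the start of SBRT

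*Combined protocol and SAP*

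**What the plan says.** Section 7.2 sets one window per group. The sequential SBRT arm has the longest: "Group 2: within 43 days of therapy initiation in the sequential arm (ipilimumab/BMS-986156/radiation". Both other groups are given 29 days, counted from the first treatment. Section 8.2.2 puts the assessment visit on day 29 or day 43.

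Section 7.2.1 lists the DLTs. For all groups they include combination toxicity "that prevents administration of ipilimumab/BMS-986156 for > 21 days and/or nivolumab/BMS-986156 for > 28 days from the scheduled dose", and a grade 3/4 rash that has not improved after infusion has been held for one to two weeks. For groups 2 and 3 the list adds any grade 3 or higher event in the radiation field. It also says that the MTD in those groups rests only on toxicity of the irradiated organ.

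Section 1 schedules ipilimumab/BMS-986156 on days 1, 22, 43 and 64 (groups 1 and 2) and nivolumab/BMS-986156 on days 1, 29, 57 and 85 (group 3). SBRT in group 2 is given "on days 29-32 for 50 Gy in 4 fractions or on days 29-40 for 60 Gy in 10 fractions". In group 3 it is given on days 1-4 (or 2-5) or days 1-12.

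The opening of Section 10 makes the cohort report due "after the first 3 evaluable patients in groups 1 and 3 complete 29 days of study treatment", and after 43 days for group 2. IND Office approval is needed before a dose level changes. Section 5.1.9 states for ipilimumab: "The median time to onset of Grade 3-5 IRAEs in MDX010-20 and Phase 2 studies was 7 to 9 weeks".

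**The concern.** A 3+3 design works only if each patient's DLT status can be settled by the time the cohort is judged. Two listed criteria need a dose to be missed and a further interval to pass, and in groups 1 and 3 that interval runs to or beyond the closing day. Such a patient can be counted as DLT-free on a criterion that could not yet be judged.

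In group 2 the issue is the irradiated-organ toxicity that is meant to drive its MTD. Radiation starts 14 days before the window closes, so this toxicity has little time to appear.

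The primary objectives are at stake: the safe dose of BMS-986156 with ipilimumab, and the safety of adding SBRT. Section 3.3 says there are no clinical data on ipilimumab with BMS-986156, and under Section 1 the group 1 DLT count decides when group 2 may open.

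**Working it through.** **The plan's own days.** With 21-day cycles, cycle 2 day 8 is 1 + 21 + 7 = day 29 and cycle 3 day 1 is 1 + 42 = day 43. With 28-day cycles, cycle 2 day 1 is 1 + 28 = day 29. Section 8.2.2 reproduces.

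**Delay criterion.** Earliest day met = scheduled day of dose 2 + permitted delay + 1.

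| Group | Calculation | First met | Window closes | Gap |
|---|---|---|---|---|
| 1 | 22 + 21 + 1 | day 44 | day 29 | 15 days late |
| 2 | 22 + 21 + 1 | day 44 | day 43 | 1 day late |
| 3 | 29 + 28 + 1 | day 58 | day 29 | 29 days late |

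Two readings were varied: dose 2 moved by 3 days either way (the allowance in Section 7), and the window counted in elapsed days, so that it ends one day later. The gap is then 11 to 18 days in group 1 and 25 to 32 days in group 3. In group 2 it runs from 3 days inside the window to 4 days outside it.

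If a first infusion stopped by a day 1 reaction counts as a prevented dose, the criterion is met on 1 + 22 = day 23 in the ipilimumab groups, inside both windows. In group 3 it is met on 1 + 29 = day 30.

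**Rash criterion, dose 2 held for one to two weeks.**
- Group 1: 22 + 7 = day 29 to 22 + 14 = day 36, at or past day 29.
- Group 2: the same days 29-36, inside day 43.
- Group 3: 29 + 7 = day 36 to 29 + 14 = day 43, past day 29.

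**Discontinuation against DLT status.** Section 7.3.4 stops treatment permanently when drug-related toxicity blocks ipilimumab/BMS-986156 for 21 days or more. For dose 2 that is 22 + 21 = day 43. A group 1 patient can therefore be taken off drug for toxicity 14 days after being counted as DLT-free.

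**Observation after SBRT.** Closing day minus SBRT day.

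| | Group 2 (closes day 43) | Group 3 (closes day 29) |
|---|---|---|
| From first fraction | 43 - 29 = 14 days | 29 - 1 = 28 days (27 if started on day 2) |
| After last, 50 Gy in 4 | 43 - 32 = 11 days (10 if it ends on day 33) | 29 - 4 = 25 days (24 if it ends on day 5) |
| After last, 60 Gy in 10 | 43 - 40 = 3 days | 29 - 12 = 17 days |

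**Onset of severe immune-related events.** Seven to nine weeks is 49 to 63 days, later than day 29 and day 43. By the meaning of a median, fewer than half of such events would have begun by either closing day. If onset were exponential, which is an assumption and not in the documents, the share would be 27-34% by day 29 and 38-46% by day 43. The source figure is for ipilimumab without BMS-986156.

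**The case against.** Much of the case on the other side stands.

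- A reader might infer that the delay criterion can never be met in any group. The documents do not support that. Group 2 misses by one day on nominal dates and meets the criterion under elapsed-day counting or an early dose 2. Its rash criterion fits inside its window.
- A reader might infer that serious slow toxicity generally escapes. Most grade 3 or higher non-skin events are DLTs under other bullets, as is any event the investigator judges a substantial risk with continued dosing. What can be lost is mainly lower-grade toxicity that holds dosing, and rash.
- Because the MTD in groups 2 and 3 rests on the irradiated organ, systemic immune-related events and rash would mostly not drive those decisions anyway. The delay, rash and onset points therefore weigh chiefly on group 1. Section 5.1.9 says nothing about group 3, which receives no ipilimumab.
- A reader might infer that planned DLT comparisons between groups 2 and 3 are invalid. Section 10.2.3 compares grade 3 or higher adverse events, Section 10.2.1 calls the comparisons exploratory, and neither limits them to the DLT window.
- A reader might want a probability that an unsafe dose is accepted. That needs a true DLT rate and a capture fraction that the documents do not give. It also differs by group: group 1 accepts on 0/3, or on 1/3 then 0/3, whereas groups 2 and 3 treat six and accept at most 1/6. With an assumed 40% rate and full, 50% or 30% capture, the rule in groups 2 and 3 accepts 23%, 66% or 84% of the time. These figures illustrate direction only.
- Late events are seen. Section 7.5 evaluates radiation reactions at later visits, Section 9.1 collects serious events to 100 days after the last dose, Section 10 repeats the safety report every three evaluable patients, and Section 10.1 has an expansion stop above 33% DLTs with a review of all DLTs.

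The last point does not close the gap, because no text found says that an event completed or arising after the window counts in the 3+3 decision. Section 7.2 also does not say whether a qualifying delay must finish inside the window or only begin there.

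**Conclusion.** The concern holds as an internal conflict between the windows, the DLT criteria and the SBRT calendar.

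The delay criterion for dose 2 falls 15 days past the window in group 1 and 29 days past it in group 3 on nominal dates, and at least 11 and 25 days past it under every variant tried for dose 2. In group 2 the one-day miss is a matter of definition. The rash criterion is at or past the window in group 1 and past it in group 3.

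Group 2 has half of group 3's observation from the first SBRT fraction (14 against 28 days), although both take their MTD from irradiated-organ toxicity. This part does not depend on how a delayed dose is read.

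The late onset of severe immune-related events is a limitation to state for the ipilimumab groups, chiefly group 1. It does not show that the windows are the wrong length.

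These conclusions rest on nominal dosing and SBRT days and on dose 2 being the first dose delayed.

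**What to change.** Reconcile Sections 7.2, 7.2.1 and 8.2.2 and the cohort report in Section 10.

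1. State that a patient whose toxicity begins inside the window is not classed as DLT-free, or reported as such, until the delay or rash criterion has been met or ruled out. Say whether days are calendar or elapsed, and whether an interrupted first dose starts the delay clock.
2. Reconcile group 2's window with its SBRT days and with the post-SBRT observation that group 3 receives. The sponsor should set the length and give the reason. If the difference is intended, say so.
3. When the safe dose is named, list events after the window that meet DLT criteria beside the 3+3 result, and state the onset limitation for the ipilimumab groups.

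The cost is protocol wording and an occasional wait for one patient's event to be settled. If group 2's window is lengthened, its cohorts clear later, and the two-weekly DLT assessments in Section 7.2 may add one visit. No extra patients are needed.
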